## ABBREVIATIONS

CDI	Clostridioides difficile infection
DSMC	Data Safety Monitoring Committee
FMT	Fecal Microbiota Transplantation
IBD	Inflammatory Bowel Disease
LYO-FMT	Lyophilized Fecal Microbiota Transplant

---

## Introduction and study rationale

*Clostridioides (Clostridium) difficile (C. difficile)* infection (CDI) is one of the most frequent causes of healthcare associated infections and its rates are also growing in the community. The attributable case fatality rate associated with CDI is 6% and there are increasing reports of treatment failures with standard therapy. CDI is also problematic as it can lead to chronic diarrhea and has been the source of outbreaks in many hospitals.

The costs associated with the management of CDI at an individual patient and at the institutional level are significant: a case of hospital-acquired CDI increases the cost of otherwise-matched hospitalization by 4-fold, which translates into annual additional costs of \$1 billion in the United States and \$100 million in Canada.

One of the major risk factors for developing this infection is taking an oral or intravenous antibiotic. The healthy bacteria, which reside within the colon are the major defense against the growth of *C. difficile* within the large intestine. Antibiotics kill these bacteria and allow *C. difficile* to multiply, produce the toxins and cause disease. The available treatments in Canada for this infection are the antibiotics metronidazole, oral vancomycin and fidaxomicin. The efficacy of these antibiotics is limited as oral vancomycin and metronidazole also suppress the growth of anaerobic bacteria such as *Bacteriodes fragilis* group which protect against proliferation of *C. difficile*. The persistent disruption of healthy colonic flora may in part explain the high frequency of recurrences following a course of treatment with these antibiotics.

Recurrence of CDI following a course of standard antibiotic therapy is high, especially in patients over 65 years of age, in hospitalized and in immunocompromised patients. As CDI and ulcerative colitis (UC) are characterized by intestinal dysbiosis, Fecal Microbiota Transplantation (FMT) has been investigated as an alternative treatment for both of these conditions. The aim of FMT is to correct the compositional and diversity imbalances of the microbial communities of the colon. Stool is collected from healthy, screened donors, and combined with water or saline solution to create a suspension that can be administered in a variety of ways, including colonoscopy, nasogastric tubes, or retention enemas.

One of the major challenges of offering FMT is the availability of suitable donors. A donor may no longer be able to continue to donate for a number of reasons and this has led to temporary interruption of FMT in centers which offered the program. In order to continue to offer FMT whenever needed, we will investigate the efficacy of lyophilized FMT. The lyophilization (freeze-drying) process works by dehydrating a frozen donor stool sample to complete dryness, using controlled temperature and pressure gradients. This lyophilized process results in a powdered form of the sample. Studies have shown that lyophilized donor stool samples depict similar microbial compositions as the same fresh sample. The technique of freeze drying has been used for decades for the industrial storage of microbes. Preliminary study of lyophilized stool for FMT has been performed in dogs. Preliminary efficacy data in dogs with inflammatory bowel disease suggest equal efficacy as compared to fresh stool, although a controlled study has yet to be performed.

Should lyophilized FMT (LYO-FMT) demonstrate to be equally or more effective than control (frozen) FMT, there would be significant advantages. As with frozen FMT, LYO-FMT will allow patients to receive FMT immediately as it can take up to two weeks for a donor's screening laboratory testing results to be available. LYO-FMT will also be more cost effective as fewer donors will need to be screened given the prolonged shelf life of LYO-FMT which can be kept at above freezing temperature. This will also allow

wider distribution and accessibility across Canada especially to regions with limited capacity to manufacture FMT.

This study is designed to be open-labeled to evaluate the efficacy of LYO-FMT (versus historical controls) as expeditiously as possible and to minimize the time and cost associated with conducting a two-armed randomized controlled trial given that the efficacy of frozen or fresh FMT is known to be 85%. The result of this trial will be useful to inform policy makers and to assist in formulating practice guidelines. The decision to pursue this open-labeled trial is based on the recent initiatives to optimize the utilization of limited resources available for conducting clinical trials. The US Food and Drug Administration and the United Kingdom's National Institute for Health Research Health Technology Assessment Programme launched guidance on adaptive research designs to increase the speed and the efficiency of clinical trials. An open-label clinical trial to add an arm to existing study is an example of such study, which can lead to rapid results with less cost. This in turn will lead to providing the "best" therapies to as many patients as possible.

## **Study hypothesis**

- Administration of 2 enemas of LYO-FMT will have similar efficacy as control (frozen-historical) FMT in reducing the rates of recurrence of CDI.

## **Study objective**

- To study the outcome of participants treated with 2 enemas of LYO-FMT for recurrent CDI

## **Study outcomes**

### **Primary endpoint**

- Evaluate treatment efficacy as determined by no recurrence of CDI-related diarrhea at 13 weeks after receiving up to 2 LYO-FMTs without the need for an intervention (antibiotics or frozen or LYO-FMT as per investigator's decision) specifically for recurrence of CDI.

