### **Secondary endpoints**

1. Evaluate treatment failure rate as defined by persistence of diarrhea and a positive *C. difficile* toxin assay or *tcdB* PCR within 5 days of the last LYO-FMT, or the need for additional intervention for CDI, colectomy or death directly due to CDI at 13 weeks following the last LYO-FMT.
2. Evaluate safety of LYO-FMT
  - Assessment for adverse reactions by history, complete blood count and chemistry panel at day 7 (+/- 3d), day 30 (+/-3d) of the study period.
  - Any serious adverse events up to and including week 13 from the 2nd FMT for any of the following:
    - Death or a life-threatening event
    - Hospitalization or prolongation of current hospitalization
    - A significant new incapacity to conduct normal life functions

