## **Study Design**

The design of this research is a multi-centre, prospective open-label (single arm) trial using LYO- FMT (treatment) to prevent recurrence of CDI in patients with history of recurrent CDI or to control diarrhea in patients with refractory CDI.

The study participants, individuals over the age of 11 years able to consent and comply with treatment. Participants required to have laboratory or pathology-confirmed diagnosis of recurrent CDI based on the Society for Healthcare Epidemiology of America (SHEA) definition, where recurrence is defined as return of diarrhea and positive stool test after a period of symptom resolution within 8 weeks of the first episode and has received at least a 10-day course of oral vancomycin.

Thirty grams of fresh stool collected within 5 hours from a healthy screened donor to be placed in a 60mL sterile container. Stool be frozen at -80°C and undergo lyophilization. Lyophilized products to be stored at 2 to 8°C for up to 112 weeks inside a box to avoid light exposure. Reconstitute LYO-FMT using 30mL normal saline. The participants received 30mL of the reconstituted lyophilized product as a retention enema using a syringe with a catheter tip. Discontinue the antibiotic 24 - 48 hours prior to the scheduled FMT. Participants to receive LYO-FMT via retention enema(s) on day 1 and the second LYO-FMT between day 5 and day 8 following the first LYO-FMT.

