### The duration of treatment and study period

Participants received LYO-FMT via retention enema(s) on day 1 and repeat on day 5 through day 8 following the first LYO-FMT.

Assess the participants at day 1 and with medical history (including concurrent medications and recent antibiotic use), clinical assessment. Reassessment, blood work, and a repeat LYO-FMT on day 5 (+3: between day 5 and 8 from the first). At study visits, assess for clinical response, treatment failure and adverse reactions by clinical assessment and laboratory test. Follow the participants at day-10, week 5 and week-13 and yearly for 2 years subsequent to the completion of treatment for any evidence of relapse, adverse event and overall health. With ongoing or recurrence of diarrhea, the participant(s) undergo medical history, physical examination, complete blood count, chemistry panel and stool for *C. difficile* toxin by EIA or PCR for *tcdB* gene. For treatment failures or relapse during the study period, participants receive repeat lyophilized or frozen FMT(s), based on the investigator's decision and availability of type of FMT or standard antibiotic therapy.

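### Read literally, the primary endpoint counts only recurrence, so a participant whose test-positive diarrhoea never resolves can be a primary success and a secondary treatment failure at once

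*Combined protocol and SAP*

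**What the plan says.** The section Primary endpoint defines efficacy as "no recurrence of CDI-related diarrhea at 13 weeks after receiving up to 2 LYO-FMTs without the need for an intervention". The interventions listed are "antibiotics or frozen or LYO-FMT as per" the investigator's decision, and they count only if given "specifically for recurrence of CDI".

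Secondary endpoint 1 is a "treatment failure rate as defined by persistence of diarrhea and a positive" toxin or gene test, with the 5-day limit counted from the final LYO-FMT. The same endpoint also counts "the need for additional intervention for CDI, colectomy or death directly due to CDI at 13 weeks following the last LYO-FMT".

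Under Study Design, "recurrence is defined as return of diarrhea and positive stool test after a period of symptom resolution". Participant inclusion criteria also require resolution, for at least 24 hours, before a return of diarrhoea counts. Both are entry definitions; no post-treatment definition is given.

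Study Design gives a second purpose, "or to control diarrhea in patients with refractory CDI", and the inclusion criteria admit, through an and/or, people with ongoing symptoms despite oral vancomycin.

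The duration of treatment and study period names two triggers for rescue: "For treatment failures or relapse during the study period, participants receive repeat lyophilized or frozen FMT(s"), or standard antibiotics.

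The sample size section sets a lowest acceptable response rate of 70% beside a historical 85%. Type of statistical analyses is one sentence on a clinical response rate and does not say which events count as non-response.

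**The concern.** Both parts of the primary endpoint depend on recurrence. Diarrhoea that never stops has not recurred, and rescue given for it is not rescue for a recurrence. For people enrolled with ongoing symptoms, the literal endpoint therefore does not measure the stated aim of controlling their diarrhoea.

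The rate compared with 70% would then include some participants whom the plan elsewhere calls treatment failures. The trial is open-label with one arm and has no written scoring rule, so the choice between readings could be made after outcomes are known.

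**Working it through.** **Step 1. Score the same events under each definition.**

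| Event after the study LYO-FMTs | Primary, literal | Primary, broader reading | Secondary endpoint 1 |
|---|---|---|---|
| Diarrhoea resolves, then CDI returns | Failure | Failure | Failure if further intervention is needed |
| Test-positive diarrhoea never resolves, rescued | Success | Failure | Failure |
| Test-positive within 5 days, never resolves, not rescued | Success | Unclear | Failure |
| Colectomy or CDI death, no recurrence and no earlier listed intervention | Success, or not stated | Not covered | Failure |
| Non-CDI death before week 13 | Not stated | Not stated | Not a failure by itself |

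The broader reading rests on the words for efficacy and response, and on the rescue list that the primary endpoint shares with the duration section. The second row is the main problem. The fourth is a small residual gap on either reading.

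**Step 2. Direction.** Moving from the broader to the literal reading turns some failures into successes and never the reverse. The observed rate can only stay the same or rise.

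**Step 3. The plan's own figure.** With p0 = 0.70, p1 = 0.85, one-sided 5% and 85% power, the single-arm formula is

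n = [1.645 × √(0.70 × 0.30) + 1.036 × √(0.85 × 0.15)]² / 0.15² = 56.1, so 57.

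With 10% attrition, 57 / 0.9 = 63.3, so 64. The stated 152 does not follow from these inputs. That is a separate matter and does not affect this point. I use 152 and 158 because they are the sizes that the plan gives.

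**Step 4. Illustration of size.** Inputs from the sample size section: the 70% bar, the 85% planned rate, one-sided 5%, N of 152 or 158, and 10% attrition (152 × 0.9 = 136.8, so 137; 158 × 0.9 = 142.2, so 142). My assumptions: an exact binomial test, because the plan names none, and a share s of participants (0 to 5%) who are failures on a full count but successes on the literal one.

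The bar c is the smallest count with P(X ≥ c | n, 0.70) ≤ 0.05. The chance of passing is P(X ≥ c | n, 0.70 + s).

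| n | c | s = 0% | 1% | 2% | 3% | 5% |
|---|---|---|---|---|---|---|
| 137 | 106 | 3.4% | 5.8% | 9.4% | 14.5% | 29.8% |
| 142 | 109 | 4.5% | 7.6% | 12.0% | 18.1% | 35.4% |
| 152 | 117 | 3.5% | 6.0% | 9.9% | 15.6% | 32.4% |
| 158 | 121 | 4.1% | 7.0% | 11.5% | 17.8% | 36.2% |

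**Step 5. Away from 70%.** At a true 85% with s = 0, the chance of passing is already 99.4% (n = 137) to 99.8% (n = 158), so misclassification changes nothing. At a true 65% with s = 3%, it is about 1.0% at n = 152. The effect matters only when the true rate is near the bar.

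**The case against.** The strongest reply is that the literal reading borrows an entry definition and applies it to an outcome. The endpoint is introduced as treatment efficacy, later sections speak of response, and few investigators would score unresolved CDI diarrhoea as a success. Part of this stands: the sponsor may well intend non-response to count. But the ordinary meaning of recurrence also implies earlier resolution, no section defines response, and the restriction to intervention for recurrence points the other way.

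A second reply is that a recurrence endpoint fits the study hypothesis, which concerns recurrence rates, and that secondary endpoint 1 reports the other events. Both statements are true. If recurrence alone is the target, the figures above are not an error rate. But that target leaves out the aim stated for refractory participants, and a secondary result does not decide which rate is set against 70%.

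Third, the affected group may be small. The objective, and part of Study Design, speak only of recurrent CDI, and no section says how many will enter with ongoing symptoms. This stands and limits what can be said about size.

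A reader might infer that the plan hides treatment failures, or that the result will be materially inflated. The documents support neither. The events are reported under secondary endpoint 1, their frequency is unknown, and diarrhoea that returns after resolving is a primary failure on every reading. Nor should colectomy and CDI death carry the same weight as persistence: they escape the broader reading only when no listed intervention came first.

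**Conclusion.** The point holds as a conflict of scoring rules. As written, the primary endpoint makes a never-resolving, rescued participant a success while secondary endpoint 1 makes the same participant a failure. The direction is certain relative to the broader reading; the amount is not known. The illustrated rise from 3.5% to 15.6% at N = 152 (3.4% to 14.5% with 137 evaluable) needs four assumptions: a 3% share, a true rate of exactly 70%, my choice of test, and a target that counts persistence as failure. At the planned 85% the decision is unaffected. This should be fixed because it concerns the primary endpoint and is cheap to settle. Confidence is medium, because a sensible broader intention is plausible but unwritten.

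**What to change.** 1. First check how the historical 85% was scored. The documents do not say, and the 70% bar is set beside it.
2. Then, before outcomes are scored, reconcile Primary endpoint, Secondary endpoints and the duration section. Primary success should require, through 13 weeks after the last of the up to two study LYO-FMTs: no test-positive CDI diarrhoea, persistent or recurrent; no additional intervention for CDI for either reason; no colectomy for CDI; and no death directly due to CDI.
3. Do not carry over the 5-day window of secondary endpoint 1 unchanged. It would make early test-positive diarrhoea that resolves unaided a permanent failure, and would miss unrescued diarrhoea first tested after day 5. The sponsor should state how each case is scored.
4. For scoring, state that the scheduled second enema is not an additional intervention, that a rescue FMT does not restart the 13-week clock, and how a non-CDI death before week 13 counts.
5. Refer to this rule under Type of statistical analyses, and keep a recurrence-only rate as a secondary result to match the hypothesis.

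The cost is a wording amendment and a short scoring rule. It mainly uses events already assessed for secondary endpoint 1 and at follow-up visits. However, the duration section ties stool testing to diarrhoea and sets no 5-day deadline, so the timing of tests needs checking. The success rate may be slightly lower, and the primary endpoint will largely overlap with secondary endpoint 1. Comparability with the 85% may improve or worsen, depending on step 1.

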### **Secondary endpoints**

1. Evaluate treatment failure rate as defined by persistence of diarrhea and a positive *C. difficile* toxin assay or *tcdB* PCR within 5 days of the last LYO-FMT, or the need for additional intervention for CDI, colectomy or death directly due to CDI at 13 weeks following the last LYO-FMT.
2. Evaluate safety of LYO-FMT
  - Assessment for adverse reactions by history, complete blood count and chemistry panel at day 7 (+/- 3d), day 30 (+/-3d) of the study period.
  - Any serious adverse events up to and including week 13 from the 2nd FMT for any of the following:
    - Death or a life-threatening event
    - Hospitalization or prolongation of current hospitalization
    - A significant new incapacity to conduct normal life functions

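### Does a day 7 (±3) safety laboratory window that straddles the second LYO-FMT leave the safety endpoint unusable?

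*Combined protocol and SAP*

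**What the plan says.** Secondary endpoints, item 2, gives the laboratory part of the safety endpoint: "Assessment for adverse reactions by history, complete blood count and chemistry panel at day 7 (+/- 3d), day 30 (+/-3d) of the study period". The same item follows serious events for longer, "Any serious adverse events up to and including week 13 from the" second FMT. Item 1 (treatment failure) ends with "death directly due to CDI at 13 weeks following the last LYO-FMT".

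Study Design puts the first LYO-FMT on day 1 and "the second LYO-FMT between day 5 and day 8 following the first LYO-FMT". The duration of treatment and study period repeats this and adds blood tests at the same visit: "Reassessment, blood work, and a repeat LYO-FMT on day 5 (+3: between day 5 and 8 from the first". It then gives a general rule, "At study visits, assess for clinical response, treatment failure and adverse reactions by clinical assessment and laboratory test", and a list of later contacts: "Follow the participants at day-10, week 5 and week-13 and yearly for 2 years subsequent to the completion of treatment".

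No listed visit is called day 7 or day 30. The order of blood draw and dose at the day 5–8 visit is not stated, although the blood work is named first. Type of statistical analyses covers only the clinical response rate and has no rule for laboratory data.

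**The concern.** The regimen under test is two doses; the Study hypothesis begins "Administration of 2 enemas of LYO-FMT will have similar efficacy". If the first safety window holds days both before and after the second dose, a result filed as day 7 may describe one dose in some participants and two in others. If the day 5–8 sample is drawn before dosing and is the only one used for day 7, the next laboratory time point in the endpoint is day 30, and the laboratory endpoint would hold no early look at the full regimen.

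Two smaller points go with it. Day 30 (±3) and week 5 may or may not be the same visit. The 13-week limits in items 1 and 2 also run from differently named doses. At stake is how clearly the safety table can be read, not the primary analysis.

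**Working it through.** **Inputs.** First LYO-FMT on day 1 and second on study day d = 5 to 8 (Study Design). Safety windows 7 ± 3 and 30 ± 3 (Secondary endpoints, item 2). Visits at days 5–8, day 10 and week 5 (The duration of treatment and study period). The plan states no figure of its own to reproduce here.

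**Step 1: windows counted from day 1.** 7 ± 3 gives days 4–10; 30 ± 3 gives days 27–33.

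| Second dose on day d | Window days before (d − 4) | Window days after (10 − d) |
|---|---|---|
| 5 | 1 | 5 |
| 6 | 2 | 4 |
| 7 | 3 | 3 |
| 8 | 4 | 2 |

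The overlap is real for every permitted dose day. If days 5 to 8 after the first dose means elapsed days, d = 6 to 9 and the split runs from 2 before and 4 after to 5 before and 1 after. The overlap remains.

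**Step 2: when is blood next taken after the second dose?** Assume that the day-10 contact is a study visit under the general rule on laboratory tests.

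- Day 10 counted from day 1: 10 − d = 2 to 5 days after the second dose (1 to 4 on the elapsed count). This lies inside days 4–10.
- Day 10 counted from the second dose: study day d + 9 or d + 10, so 14–18 (15–19 on the elapsed count). This is 9 or 10 days after the dose. It lies outside days 4–10, but the sample is still collected.
- The long gap arises only if the day-10 result is left out: 27 − 8 = 19 to 33 − 5 = 28 days (18 to 27 on the elapsed count).

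**Step 3: one origin for both lists.** The mismatch at day 10 comes from counting the windows from one dose and the visits from another. If both are counted from day 1, day 10 is the last day of the window and follows the second dose for every permitted d. If both are counted from the second dose, the window is d + 3 to d + 9 (dose day = 1) or d + 4 to d + 10 (dose day = 0). The day-10 visit is again its last day, and the window no longer straddles the dose. On either common origin, a sample after both doses falls inside the day 7 window.

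**Step 4: day 30 and week 5.** As a single day from day 1, week 5 is day 35 or 36, which is 35 − 33 = 2 or 36 − 33 = 3 days past the window. From the second dose it is study day 39–43, or 6–10 days past (7–11 on the elapsed count). Read as the calendar week of days 29–35, it overlaps the window on days 29–33. The plan gives week 5 no window, so no conflict is shown.

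**Step 5: the 13-week anchors.** For anyone given exactly two doses, the second FMT and the last LYO-FMT are the same. They differ for a participant who receives only one dose, and for one given repeat LYO-FMT after failure or relapse, which The duration of treatment and study period allows. In the second group, a repeat given for CDI is itself an additional intervention, which item 1 already counts as failure, so the choice of anchor does not change that classification. The serious-event period for that group is still defined by the second FMT. For a participant with one dose, the only workable anchor is that dose.

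**The case for a change.** The strongest case for a change is that the trial is multi-centre and nothing in the text stops sites from filing different visits as day 7. One column could then mix results after one dose with results after two. Blood work is listed ahead of the repeat dose, which suggests a sample that reflects one dose only. The clarification would cost a sentence or two and, if day 10 is counted from day 1, no extra blood draw.

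The labelling gap stands, and so does the arithmetic behind the overlap. The consequence does not. Item 2 describes surveillance for reactions by history and laboratory panel. It defines no single day 7 value, no change from baseline and no test, so an analyst need not choose one sample and discard the other. The 19–28 day gap requires setting aside a sample that the plan itself schedules. A mixed column is avoided by the ordinary practice of listing safety laboratory data by visit, with dose and draw dates showing how many doses came first. Clinical assessment for reactions and serious-event follow-up also run alongside the laboratory panel, so detecting harm does not depend on which sample carries the label.

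**Conclusion.** The concern does not call for a change. The day 7 window does span the second dose when counted from day 1, and the plan does not link its safety time points to its visits. This is missing detail that analysts fill sensibly by tabulating by visit. Followed as written, the plan yields blood results at the second-dose visit and again 1–5 days after that dose, or 9–10 days after it, depending on how day 10 and the dose interval are counted. The week 5 question is an ambiguity of 2–3 days from day 1, up to 11 days on the widest reading, and none if week 5 is a calendar week. The anchor wording matters only for participants without exactly two doses; the documents do not say how many there will be.

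This rests on three assumptions: the day-10 contact is a study visit with laboratory tests, dose and draw dates are recorded, and safety laboratory data are reported descriptively. It takes no position on which day count or dosing interval is intended. The primary endpoint, sample size, power and significance level are unaffected.
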